4.4.4. Vital Signs and Physical Examination

The actual value and change from baseline (Day 1) to each on-study evaluation and to the last on study evaluation will be summarized for vital signs.

A summary table of the number and percent of patients with treatment-emergent potentially clinically significant (PCS) vital signs parameters will be tabulated based on the following criteria:

Variable Name	PCS – Low if:			PCS – High if:		
	Observed Value is:	AND	Decrease from Baseline is:	Observed Value is:	AND	Increase from Baseline is:
Systolic Blood Pressure	<90 mmHg		≥ 20 mmHg	>180 mmHg		≥ 20 mmHg
Diastolic Blood Pressure	<50 mmHg		≥ 10 mmHg	>105 mmHg		≥ 10 mmHg
Heart Rate	<50 bpm		≥ 15 bpm	>120 bpm		≥ 15 bpm

PCS= potentially clinically significant.

All tables summarizing vital sign measurements only include visits in which at least 10% of the analysis population had measurements. Vital sign measurements will be presented for each patient in a data listing.

All physical examination findings and ECOG performance status findings will be tabulated by visit and presented in data listings.

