9.3.5 Study Day 21 ± 3 Days

- Concomitant medication assessment
- Clinical laboratory tests: hematology, serum electrolytes and chemistry (including albumin), coagulation parameters, and urinalysis
- Monitoring for changes in visual acuity and color vision
- AE and SAE monitoring

9.3.6 Study Day 28 ± 3 Days, Then Every 7 ± 3 days: Delayed End of Cycle for Toxicity Resolution Only if Required

- Concomitant medication assessment
- ECOG PS
- Physical examination
- Vital signs and weight
- 12-lead ECG
- Clinical laboratory tests: hematology, serum electrolytes and chemistry (including albumin), coagulation parameters, and urinalysis
- Collection of peripheral blood (serum) for immunogenicity

- AE and SAE monitoring

9.4 Cycles 2 – 6

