3. GENERAL STATISTICAL METHODS

3.1. Sample Size Justification

Approximately 21-33 adult patients diagnosed with AML that is considered high-risk disease who have achieved a first or second CR or complete remission with incomplete bone marrow recovery (CRi) within 6 months prior to enrollment and are not considered immediate candidates for allogenic stem cell transplant (SCT). The anticipated sample size is sufficient to evaluate the primary objectives.

During Stage 1, approximately 9-18 patients will be treated with Tagraxofusp.

In Stage 2, up to 20 additional patients with MRD as determined locally will enroll and receive Tagraxofusp at either the MTD or maximum tested dose, so that a total of 15 patients with evidence of MRD, as determined centrally, are treated at this dose. The assumptions governing sample size are as follows:

- Null hypothesis: eradication of MRD $\leq 5\%$
- Alternate hypothesis: eradication of MRD $\geq 20\%$
- Type 1 error: 17% one-sided
- Power: $>80\%$

Because no available anti-leukemia therapies (other than allogeneic transplant) are believed to be associated with the eradication of evidence of MRD in this high-risk AML setting, the study would be considered positive if ≥ 2 of 15 patients in 1st remission are converted from MRD-positive to MRD-negative status. (In a situation where 1 of 15 patients has eradication of MRD, the results may be considered of interest, given the dearth of efficacious therapy in this setting).

At the time of database lock, in Stage 1, 18 patients were enrolled. In Stage 2, 9 patients with MRD were enrolled.

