4.4.3. Laboratory Data

Clinical laboratory values will be expressed in Système International (SI) units.

The actual value and change from baseline (Day 1) to each on-study evaluation through cycle 6 will be summarized for each clinical laboratory parameter, including hematology, clinical chemistry, coagulation, and urinalysis. In the event of repeat values, the last non-missing value per study day/time will be used.

[figure not shown]
Shift tables of change in CTCAE grade of laboratory parameters from baseline to worst value and from baseline to last value on study will be presented. Both scheduled and unscheduled visits will be included in shift tables.

To assess for possible drug-induced liver injury ([FDA 2009](#)), a figure plotting peak alanine aminotransferase (ALT) versus peak total bilirubin (both on a logarithmic scale \times upper limit of normal [ULN]) will be produced similar to that recommended by Watkins et al ([Watkins, et al. 2008](#)) so that values within the normal reference range (<ULN) for ALT and total bilirubin are found in the left lower quadrant and Hy's Law case candidates are in the upper right quadrant (ALT $>3 \times$ ULN and total bilirubin $>2 \times$ ULN). Patients with Gilbert's syndrome or cholestasis are typically found in the upper left quadrant, and patients with ALT elevations without significant hepatic abnormality (ie, without increased total bilirubin) are found in the lower right quadrant. The peak total bilirubin value plotted will be the peak within ± 7 days of the peak ALT value. If at least five patients are identified as potential Hy's Law Cases, a summary table will be produced for the number and percentage of patients who have values of aspartate aminotransferase (AST) (>3 to $\leq 5 \times$ ULN, >5 to $\leq 10 \times$ ULN, >10 to $\leq 20 \times$ ULN, $>20 \times$ ULN), ALT (>3 to $\leq 5 \times$ ULN, >5 to $\leq 10 \times$ ULN, >10 to $\leq 20 \times$ ULN, $>20 \times$ ULN), alkaline phosphatase ($>1.5 \times$ ULN), or total bilirubin (>1.5 to $\leq 2 \times$ ULN, $>2 \times$ ULN) after initiation of study drug. In this table, a patient may be counted only one time. For instance, a patient with a result of AST of $11 \times$ ULN will be counted in the category of >10 to $\leq 20 \times$ ULN.

This plot will be repeated for peak aspartate aminotransferase (AST) by total bilirubin.

An example of the scatterplot is provided in [Figure 4-1](#).

Figure 4-1: Hy's Law Candidates Scatterplot

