4.4.5. Electrocardiogram

ECG results will be summarized descriptively, including the number and percentage of patients with normal, abnormal, and clinically significant abnormal results at baseline and each study visit. Actual values and change from baseline will be summarized for QTc intervals. All tables summarizing ECG measurements only include visits in which at least 10% of the analysis population had measurements

The number and percentage of patients whose mean QTcF or QTcB value at any time point meets any of the following categories will be summarized:

- >450 msec
- >480 msec
- >500 msec
- increase from baseline >30 msec
- increase from baseline >60 msec

QTcF and QTcB will be derived using QT interval and heart rate using the formulas:

$$QTcF = \frac{QT \text{ Interval}}{Heart \text{ Rate}^{1/3}} \quad QTcB = \frac{QT \text{ Interval}}{Heart \text{ Rate}^{1/2}}$$

ECG and echocardiogram/multigated acquisition scan (MUGA) data for each patient will be provided in data listings.

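### The SAP's 10% visit filter, read literally, also applies to the patient-level PCS vital-sign count and leaves the QTc category count ambiguous

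*SAP*

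**What the plan says.** SAP 4.4.4 plans two kinds of vital-sign table. One is by visit: actual value and change from baseline. The other is by patient: "A summary table of the number and percent of patients with treatment-emergent potentially clinically significant (PCS) vital signs parameters will be tabulated" against fixed thresholds, for example systolic pressure below 90 mmHg with a fall of at least 20 mmHg. After the thresholds comes the filter: "All tables summarizing vital sign measurements only include visits in which at least 10% of the analysis population had measurements".

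SAP 4.4.5 has the same filter for ECGs: "All tables summarizing ECG measurements only include visits in which at least 10% of the analysis population had measurements". The next paragraph defines a patient-level QTc table: "The number and percentage of patients whose mean QTcF or QTcB value at any time point meets any of the following categories will be summarized".

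SAP 4.4.3 treats laboratory data differently. Its shift tables run to the worst and the last value, and "Both scheduled and unscheduled visits will be included in shift tables". Vital signs and ECGs have no such sentence.

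SAP 3.11 tabulates data by the visit recorded on the eCRF, without re-windowing. SAP 4.4 presents safety tabulations by dose received, and SAP 3.5 adds overall safety summaries by stage. On numbers, SAP 3.1 reports: "At the time of database lock, in Stage 1, 18 patients were enrolled. In Stage 2, 9 patients with MRD were enrolled".

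**The concern.** The two kinds of table do different jobs. In a by-visit table of means, leaving out a visit with one or two patients is ordinary housekeeping. A patient-level outlier table asks whether a patient ever crossed a threshold on treatment, and the answer should not depend on how many other patients were measured at the same visit.

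Some visits in this trial exist because of toxicity. The visit headed "Delayed End of Cycle for Toxicity Resolution Only if Required" (Protocol 9.3.6 and 9.4.6, Tables 5 and 6) collects vital signs and an ECG. Dosing can run to Day 10 when infusions are held, and the reasons for holding include vital-sign abnormalities (Protocol 7.5.5.1.1 and 7.5.5.6). Readings may also be taken at unscheduled visits.

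Characterizing safety at the MTD or maximum tested dose is a primary objective. Hypotension is a listed sign of capillary leak syndrome, the principal DLT in Study 50047 (Protocol 3.6.3). An understated count of low systolic pressures would therefore matter to a reader of the safety tables.

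**Working it through.** The plan gives no figure to reproduce here. The check turns the 10% into patient numbers and asks how often a visit would be lost.

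**Inputs**
- Threshold: 10% of the analysis population (SAP 4.4.4 and 4.4.5).
- Patients: 18 + 9 = 27 enrolled (SAP 3.1), assumed all treated and so equal to the Safety Population.
- Denominator: not stated. Overall, stage and dose group are all possible.
- Attendance q, the chance that a given patient has a reading at a given visit: not in the documents, so a range is assumed.

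**Step 1. Patients needed to keep a visit:** m = 0.10 × N, rounded up.

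| N | 0.10 × N | Needed (m) | Most patients at a dropped visit |
|---|---|---|---|
| 27 (all enrolled) | 2.7 | 3 | 2 (2/27 = 7.4%) |
| 18 (Stage 1) | 1.8 | 2 | 1 (1/18 = 5.6%) |
| 10 | 1.0 | 1 | 0 |
| 9 (Stage 2) | 0.9 | 1 | 0 |

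In any group of 10 or fewer, one patient is enough to keep a visit, so the rule removes no data.

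**Step 2. Chance that a visit with data is dropped, N = 27.** With X ~ Binomial(27, q), this is [P(X ≤ 2) − P(X = 0)] / [1 − P(X = 0)]. A visit with no readings has nothing to lose, hence the conditioning.

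| q | P(X ≤ 2) | P(X = 0) | Dropped, given at least one reading |
|---|---|---|---|
| 5% | 0.850 | 0.250 | 0.80 |
| 10% | 0.485 | 0.058 | 0.45 |
| 15% | 0.207 | 0.012 | 0.20 |
| 20% | 0.072 | 0.002 | 0.07 |
| 30% | 0.005 | below 0.001 | 0.005 |

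The 5% row: (0.850 − 0.250) / (1 − 0.250) = 0.600 / 0.750 = 0.80. The rule bites on rare visits and fades quickly once about a fifth of patients attend.

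**Step 3. Bound on the PCS count.** At N = 27, one dropped visit hides at most 2 patients, and two hide at most 4 (4/27 = 14.8%). These bounds are reached only if every such patient had a PCS value there and none at a retained visit.

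**Step 4. The two ECG sentences.** The filter covers every ECG table. The category count takes a value "whose mean QTcF or QTcB value at any time point meets any of the following categories will be summarized". For a QTc value at a visit with 1 or 2 of 27 patients, the first sentence excludes it and the second includes it. Two programmers could produce different tables and each cite the SAP.

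**The case against.** The strongest reply is that the practical loss may be small or nil, and much of it stands.

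- **Visit labels are unknown.** Tables 5 and 6 put infusion days in one treatment column running up to Day 10, and Protocol 8.12 indexes PK sampling by infusion number. A delayed infusion may therefore share a label with everyone else's and pass the filter. Unscheduled readings pooled under one label might pass too.
- **Attendance may be well above 10%.** A fall in albumin is a reason to hold an infusion (Protocol 7.5.5.1.3), and hypoalbuminemia was attributed to SL-401 in 58.7% of Study 50047 patients (Protocol 3.6.1). That is not a hold rate, but it makes frequent holds plausible, and at q of 20% or more the loss is slight.
- **The data survive elsewhere.** Every reading is listed by patient, and findings needing intervention or further investigation are adverse events (Protocol 10.1.1). The adverse-event and capillary leak summaries have no visit filter. This is not a complete backstop, because a reading can meet the PCS thresholds without becoming an adverse event.
- **The laboratory rule governs laboratory tables only.** The difference from SAP 4.4.3 is a contrast, not a contradiction.
- **The QTc wording may already prevail.** The category table stands in its own paragraph after the filter, so its more specific wording can be read as governing.

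A reader might infer that the rule strips out the very visits where hypotension, tachycardia or QTc outliers are most likely to be recorded. The documents do not support that. Vital signs are taken up to 240 minutes after each infusion on dosing days, which in Cycle 1 easily pass 10%. Capillary leak syndrome is expected 3 to 8 days after treatment starts (Protocol 7.5.5.1), which partly overlaps those days. The rule also drops late cycles reached by one or two patients, and it keeps any toxicity visit shared by three or more of 27.

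None of this supplies the missing exemption for the PCS table.

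**Conclusion.** The point holds for the PCS vital-sign table as a literal reading of SAP 4.4.4: a patient whose only PCS value falls at a visit with data on 1 or 2 of 27 patients is omitted. For the QTc category table, the finding is an ambiguity in SAP 4.4.5; a certain loss of QTc outliers is not shown.

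The size is at most 2 patients (7.4%) per dropped visit at N = 27, at most 1 (5.6%) at N = 18, and none in groups of 10 or fewer. This assumes that all enrolled patients were treated and that affected patients have no outlier at a retained visit. How many visits would be dropped cannot be settled, because the denominator, the eCRF visit labels and the attendance rates are not given. The attendance values above are illustrative.

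The effect is confined to the outlier summary tables. The primary objective is not undermined, but those counts would rest on an irrelevant condition. The correction is worth making because it is specific and cheap.

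**What to change.** 1. In SAP 4.4.4 and 4.4.5, limit the 10% rule to the by-visit tables of actual values, changes from baseline and ECG result categories.
2. State that the PCS vital-sign table and the QTcF/QTcB category table use all readings after the first dose, scheduled and unscheduled, as SAP 4.4.3 does for laboratory shift tables.
3. State the denominator of the 10%: the whole Safety Population, the stage or the dose group.

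The cost is about one sentence in each section plus the definition of the denominator. The readings are already collected and listed, so no new data are needed. The downside is that outlier counts may rise slightly.

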4.4.5. Electrocardiogram

ECG results will be summarized descriptively, including the number and percentage of patients with normal, abnormal, and clinically significant abnormal results at baseline and each study visit. Actual values and change from baseline will be summarized for QTc intervals. All tables summarizing ECG measurements only include visits in which at least 10% of the analysis population had measurements

The number and percentage of patients whose mean QTcF or QTcB value at any time point meets any of the following categories will be summarized:

- >450 msec
- >480 msec
- >500 msec
- increase from baseline >30 msec
- increase from baseline >60 msec

QTcF and QTcB will be derived using QT interval and heart rate using the formulas:

$$QTcF = \frac{QT \text{ Interval}}{Heart \text{ Rate}^{1/3}} \quad QTcB = \frac{QT \text{ Interval}}{Heart \text{ Rate}^{1/2}}$$

ECG and echocardiogram/multigated acquisition scan (MUGA) data for each patient will be provided in data listings.

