7.5.5.6 Tachycardia, Bradycardia, or Hypertension

Withhold SL-401 infusion for patients with a heart rate ≥ 130 or heart rate ≤ 40 bpm or systolic BP ≥ 160 mmHg until resolution.

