8.7 Electrocardiograms

All patients will have a 12-lead ECG performed at the screening visit and pre-treatment visit (Study Day 0 or 1), as well as on Day 28 (\pm 3 days, and Day 35 [\pm 3 days] only if delayed end of cycle) of each cycle. During the days when patients are undergoing PK sampling (Cycles 1 and 3, infusions 1 and 5), an ECG will be performed at 3 distinct time points (triplicates) within 5 minutes prior to each PK sample collection pre-infusion and at 30 and 60 minutes post-infusion (see [Table 7](#)). An ECG should be performed after patient is supine for 5 minutes. All ECGs will be analyzed locally.

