3.4. Baseline Definitions

For all analyses, baseline will be defined as the most recent measurement prior to the first administration of study drug.

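### The QTc outlier counts in SAP 4.4.5 are not limited to post-dose ECGs or to patients below the limit at baseline, and may let either QTcF or QTcB qualify a patient (minor)

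*SAP*

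**What the plan says.** SAP 4.4.5 sets the counting rule: "The number and percentage of patients whose mean QTcF or QTcB value at any time point meets any of the following categories will be summarized". There are five categories: three absolute limits (>450, >480 and >500 msec) and two changes, of which the smaller reads "increase from baseline >30 msec" and the larger is the same at 60 msec. No post-dose window and no baseline condition is attached to the absolute limits.

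The same section introduces the corrections with "QTcF and QTcB will be derived using QT interval and heart rate using the formulas" and prints QT divided by heart rate to the power 1/3 (QTcF) and 1/2 (QTcB). It also plans summaries of QTc values and of change from baseline, counts of normal, abnormal and clinically significant abnormal ECGs by visit, and by-patient listings.

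Under SAP 3.4, "baseline will be defined as the most recent measurement prior to the first administration of study drug". Protocol 8.7, 9.2 and 9.3 provide ECGs at screening, at the pre-treatment visit and before infusion 1. Inclusion criterion 9 (Protocol 5.2) excludes clinically significant ECG abnormalities but sets no numeric QTc limit.

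By contrast, the outlier table in SAP 4.4.4 is for "treatment-emergent potentially clinically significant (PCS) vital signs parameters" and requires both a limit value and a change from baseline.

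**The concern.** Two features of the rule let patients into the table for reasons other than a longer QT after dosing.

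- **Timing and baseline.** A patient at, say, 455 msec at screening meets >450 at a time point, and so is counted even if nothing changes after SL-401.
- **Choice of correction.** If one count is made in which either correction suffices, a faster heart rate can qualify a patient through QTcB while QTcF stays flat.

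The trial has no control arm to show the background rate. SAP 3.1 records 18 + 9 = 27 patients enrolled, so one patient is 1/27 = 3.7% and a few such entries change a reported percentage visibly.

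**Working it through.** The plan gives no expected figure for this table, so there is none to reproduce. The counting rule, categories and printed formulas come from SAP 4.4.5. All QT, QTcF and heart-rate (HR) values below are assumptions.

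**1. Formulas as printed, HR in bpm (the unit used in SAP 4.4.4).** Take QT 400 msec.
- At 75 bpm: QTcF = 400/75^(1/3) = 95 and QTcB = 400/75^(1/2) = 46.
- At 120 bpm: QTcF = 81 and QTcB = 37.
- To exceed 450 msec at 75 bpm, QT would have to exceed 450 × 75^(1/3) ≈ 1,898 msec (QTcF) or 450 × 75^(1/2) ≈ 3,897 msec (QTcB).

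The absolute categories would be empty, and a faster heart rate would lower both values. The heart-rate point therefore arises only once RR = 60/HR (seconds) is the divisor. The timing and baseline point is a matter of wording and does not depend on the formula.

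**2. Formulas with RR.** QTcF = QT/RR^(1/3) and QTcB = QT/RR^(1/2). Hence QTcB/QTcF = RR^(−1/6) = (HR/60)^(1/6).

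Hold QTcF at 410 msec:
- 70 bpm: 410 × 1.0260 = 420.7
- 110 bpm: 410 × 1.1063 = 453.6
- Difference: 32.9 msec

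Both >450 and >30 msec are met with no change in QTcF.

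**3. Which categories are exposed.** QTcB reaches a limit L when HR = 60 × (L/QTcF)^6.

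| Constant QTcF (msec) | HR for 450 | HR for 480 | HR for 500 |
|---|---|---|---|
| 410 | 105 | 155 | 197 |
| 420 | 91 | 134 | 171 |
| 430 | 79 | 116 | 148 |

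For changes from 70 bpm at QTcF 410, HR = 60 × (1.0260 + d/410)^6. This gives about 106 bpm for d = 30 and about 156 bpm for d = 60. Ordinary increases in rate can produce >450 and >30; >500 and >60 need extreme rates.

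**4. Illustrative frequencies with no drug effect on QTcF.** Assumed: QTcF mean 412 msec, between-patient SD 15, within-patient SD 6, eight on-treatment time points, baseline HR mean 75 (SD 8), and on-treatment mean HR 75, 85 or 95. On-treatment HR is drawn in two ways: independently of the patient's own baseline with SD 12, or tied to that baseline with within-patient SD 6.

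| Category | QTcF alone | Either, independent HR (75/85/95) | Either, tied HR (75/85/95) |
|---|---|---|---|
| >450 | about 3% | 38/56/72% | 27/45/63% |
| >30 increase | 0.2% | 16/35/59% | 1/12/43% |
| >500 | – | 0.1/0.4/1.4% | – |
| >60 increase | – | 0.1/0.3/1.5% | – |

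In 27 patients, >450 is about 1 by QTcF alone (0.03 × 27 = 0.8). By either correction it is about 10 to 19 with independent HR (0.38 × 27 = 10.3; 0.72 × 27 = 19.4) and about 7 to 17 with tied HR (0.27 × 27 = 7.3; 0.63 × 27 = 17.0).

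**5. Pre-dose values under the same assumptions.** About 11% exceed 450 before dosing by either correction and about 1% by QTcF alone. Adding the baseline ECG to the eight on-treatment ones moves the either-correction >450 count only from 37.8% to 38.6% (independent HR, mean 75). Limiting the table to post-dose ECGs therefore changes little by itself; separating the corrections and conditioning on baseline matter more.

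**The case against.** The strongest reply is that this is one descriptive table among several. SAP 4.4.5 already plans QTc values, changes from baseline, ECG classification by visit and listings, so a reader can identify pre-existing values and flat QTcF. QT is not a study objective, and the dose-limiting toxicity definition names no QTc limit. The SAP does not call the counts drug-related. All of this stands, and it is why the point is minor.

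Two further objections hold in part. The word *or* fits separate tabulation of QTcF and QTcB as well as a combined count, and no table shell settles which is meant. That makes the text ambiguous, which still needs resolving before programming. Also, the formulas as printed would empty the absolute categories rather than inflate them. That is a separate error that must be corrected for the table to work, and correcting it is what exposes the either-correction problem.

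A reader might infer that SL-401 will raise heart rate and so fill the table. The documents give no on-treatment heart-rate data. Fever was attributed to SL-401 in 29.3% of patients in Study 50047 (Protocol 3.6.1), but that is any grade and is not tied to ECG times. The rule in Protocol 7.5.5.6 to withhold for "heart rate ≥ 130 or heart rate ≤ 40 bpm or systolic BP ≥ 160 mmHg until resolution" covers slow rates and hypertension as well. ECGs are taken supine (Protocol 8.7), and infusions follow acetaminophen premedication (Protocol 7.5.3.1). A heart-rate rise is possible but not established.

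**Conclusion.** The point holds as a minor defect in a descriptive safety table. It is plain from the text that the three absolute limits carry no post-dose or baseline condition, unlike SAP 4.4.4. The >30 and >60 msec categories do not share that fault. It is a permitted reading, not a settled one, that either correction alone can qualify a patient.

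With RR as the divisor, the link between QTcB and QTcF is exact: at a constant QTcF of 410 msec, 70 to 110 bpm adds 33 msec to QTcB. How many patients that would add is not known. The illustrative frequencies rest wholly on assumed values and shift markedly with how heart rate is modelled, especially for >30 msec. The effect falls mainly on >450 and >30 and is negligible for >500 and >60.

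A reader might conclude that the trial will report heart-rate artefact as QT prolongation on SL-401, or that a true QTcF signal could not be told apart from it. The documents do not support that, because other QTc displays are planned and the counts are not labelled as drug effects.

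**What to change.** Amend SAP 4.4.5 in the same edit that makes RR = 60/HR (seconds) the divisor in both formulas:

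1. Tabulate QTcF and QTcB separately, and name QTcF as the basis for interpretation.
2. Restrict all five categories to ECGs after the first infusion.
3. For >450, >480 and >500 msec, either present a shift table from baseline category to worst post-dose category, or count only patients not above that limit at baseline, with the denominator stated.

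The cost is SAP wording and the re-layout of one table. No new data are needed.

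### SAP 4.4.5 divides QT by a power of heart rate instead of the RR interval, so the three absolute QTc categories can never be met and the change-from-baseline categories are distorted

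*SAP*

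**What the plan says.** SAP section 4.4.5 (Electrocardiogram) gives the only QTc derivation in either document. It says "QTcF and QTcB will be derived using QT interval and heart rate using the formulas" and prints two fractions: QT interval over heart rate to the power 1/3 for QTcF, and over heart rate to the power 1/2 for QTcB. Neither document mentions an RR interval or a 60/HR conversion.

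The same section puts the results to two uses. Actual QTc values and their change from baseline are summarized. In addition, "The number and percentage of patients whose mean QTcF or QTcB value at any time point meets any of the following categories will be summarized": three absolute limits (above 450, 480 and 500 msec) and two changes, "increase from baseline >30 msec" and "increase from baseline >60 msec".

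The section gives no unit for heart rate. Elsewhere the unit is bpm: in the vital-signs table of SAP 4.4.4, and in protocol 7.5.5.6 ("Withhold SL-401 infusion for patients with a heart rate ≥ 130 or heart rate ≤ 40 bpm").

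SAP 4.4.5 also plans a count of ECGs by overall reading (normal, abnormal, clinically significant abnormal). That count does not use the formulas. Protocol 8.7 has ECGs read locally, with triplicates before infusions 1 and 5 of Cycles 1 and 3 and at 30 and 60 minutes afterwards.

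**The concern.** The exponents 1/3 and 1/2 and the suffixes F and B identify the Fridericia and Bazett corrections, which divide QT by a power of RR in seconds. Heart rate is the reciprocal of RR apart from a constant. Putting it in the denominator therefore does two things: it moves the result to a different scale, and it reverses the correction, so that a faster heart rate lowers QTc instead of raising it.

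At stake is the quantitative QTc part of the safety report. ECGs are a listed safety assessment (protocol 11.4, SAP 1.2.5.2), and the triplicate schedule is there to detect changes around infusion. If programmed as printed, the absolute-category table would report nobody above 450 msec whatever the data.

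**Working it through.** **Inputs.** Formulas and category limits: SAP 4.4.5. Heart rate in bpm: SAP 4.4.4 and protocol 7.5.5.6. The heart-rate range 40-130 bpm is taken from the two limits in protocol 7.5.5.6. The QT range 300-550 ms is an assumption. The plan states no QTc result, so there is no figure to reproduce.

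**Formulas compared.**
- Printed: F = QT/HR^(1/3); B = QT/HR^(1/2).
- RR-based: F = QT/(60/HR)^(1/3); B = QT/(60/HR)^(1/2).

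**1. Scale.** At 60 bpm, 60^(1/3) = 3.915 and 60^(1/2) = 7.746, so printed values are about a quarter and an eighth of QT.

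| QT (ms) | HR (bpm) | Printed F | Printed B | RR-based F | RR-based B |
|---|---|---|---|---|---|
| 400 | 60 | 102.2 | 51.6 | 400 | 400 |
| 400 | 80 | 92.8 | 44.7 | 440 | 462 |
| 400 | 100 | 86.2 | 40.0 | 474 | 516 |
| 450 | 80 | 104.4 | 50.3 | 495 | 520 |
| 520 | 60 | 132.8 | 67.1 | 520 | 520 |

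Over the whole assumed range, printed F runs from 59.2 (QT 300 at 130 bpm) to 160.8 (QT 550 at 40 bpm), and printed B from 26.3 to 87.0. With QT fixed at 400, the printed values fall as heart rate rises, while the RR-based values rise.

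**2. Absolute categories.** To exceed 450 at 60 bpm, QT would have to exceed 450 × 3.915 = 1,762 ms (F) or 450 × 7.746 = 3,486 ms (B), although one whole beat lasts 60,000/60 = 1,000 ms. At 40 bpm, the most favourable rate in the range, F still needs QT above 1,539 ms against an RR of 1,500 ms. So none of the three limits can be reached.

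**3. Change categories, constant 60 bpm.**
- >30 msec needs a raw QT rise above 30 × 3.915 = 117 ms (F) or 30 × 7.746 = 232 ms (B).
- >60 msec needs a rise above 235 ms (F) or 465 ms (B).
- A rise from QT 400 to 500 is a true 100 ms but prints as 25.5 (F) and 12.9 (B).

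**4. Change categories, heart rate moving.**

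| From | To | Printed F / B | RR-based F / B |
|---|---|---|---|
| QT 400, 60 bpm | QT 420, 90 bpm | −8.5 / −7.4 | +80.8 / +114.4 |
| QT 340, 100 bpm | QT 440, 55 bpm | +42.4 / +25.3 | +24.3 / −17.7 |
| QT 320, 110 bpm | QT 440, 50 bpm | +52.6 / +31.7 | +22.4 / −31.6 |
| QT 340, 100 bpm | QT 480, 50 bpm | +57.0 / +33.9 | +48.6 / −0.8 |

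The first row is a real rise reported as a fall. The second (on F) and third (on both) exceed 30 msec although the RR-based change does not. The last row gives the largest printed change among the pairs tried. A change above 60 is not arithmetically impossible: the extreme corners of the assumed range differ by 160.8 − 59.2 = 101.6 on F. But that needs heart rate to fall from 130 to 40 bpm while QT goes from 300 to 550 ms.

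**5. Can a different unit rescue the formulas?** With heart rate in beats per second, QT 400 at 60 bpm returns 400. But QT 400 at 100 bpm returns 337 (F) and 310 (B), where the RR-based values are 474 and 516. The scale is restored and the direction is still wrong.

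**The case against.** The best defence is that the error is conspicuous and confined. Mean QTc values of roughly 40-110 ms would look absurd in the summary of actual values, and a programmer using a standard routine would probably compute the right quantity. Local ECG reading, the overall ECG classification and the by-patient listings offer other routes to a prolonged QT. QT prolongation is not named in the primary objectives, is not an adverse event of special interest (SAP 4.4.2, protocol 10.1.1) and has no DLT criterion of its own (protocol 6.2.1.1). Protocol 11.4 asks only for descriptive ECG summaries.

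Most of that stands, and it limits the reach of the point. It does not make the text right. The sentence and both formulas agree with each other, so a PDF reading fault is not a credible explanation. The SAP specifies no plausibility check on QTc. Silently programming other formulas would depart from the SAP, and SAP section 5 requires deviations to be documented.

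A reader might go further and infer that no patient could ever be flagged, that all five categories would show about 0%, and that the study would report a falsely clean QT profile. The documents do not support that. Only the three absolute categories are necessarily empty. The >30 msec category can be met when heart rate slows, so it errs in both directions. The overall ECG classification does not pass through the formulas. Nor do the documents show that any QTc output has been produced with them: the section is written in the future tense.

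**Conclusion.** The formulas are wrong as written. The three absolute categories would be empty for every patient. The >30 msec category misses real rises and can raise spurious flags, and the >60 msec category is practically out of reach. The planned summaries of actual QTc and change from baseline are invalid.

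The empty absolute categories follow from the SAP's own limits, given heart rate in bpm. The quoted ranges of printed values rest on the assumed QT of 300-550 ms and heart rate of 40-130 bpm. The reversed direction depends on neither the unit nor those ranges.

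The damage is limited to the descriptive QTc output. Dose escalation, the MTD, the MRD test and the overall ECG classification are not affected. Correction is still required before the QTc tables are relied on, because as specified they cannot do what they are for.

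**What to change.** In SAP 4.4.5, replace the two formulas with QTcF = QT/(60/HR)^(1/3) and QTcB = QT/(60/HR)^(1/2). State that QT is in msec and HR in bpm, and adjust the lead-in sentence to name RR = 60/HR in seconds.

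Check the programmed derivation against the corrected text with two test records: QT 400 at 60 bpm must return 400 for both, and QT 400 at 100 bpm must return 474 (F) and 516 (B). Rerun any QTc table or listing that used the printed formulas, and record the change as SAP section 5 requires.

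The cost is a short text correction and a check of one derivation, plus a rerun if outputs already exist. No new data are needed, because QT and heart rate are already the planned inputs.
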